### 12.2.5.2. CTCAE V3.0 gradings for biochemistry tests

CTCAE version 3.0 classification is only for the below tests. For other tests, only the classification according to normal ranges will be done.

Lab test	Grade 0	Grade 1	Grade 2	Grade 3	Grade 4
Albumin (g/L)	≥ LLN	[30,LLN[	[20,30[	<20	(NAP)
ALT, AST, alkaline phosphatase and γGT	≤ ULN	]1.0,2.5] x ULN	]2.5,5.0] x ULN	]5.0,20.0] x ULN	> 20.0 x ULN
Amylase and lipase	≤ ULN	]1.0,1.5] x ULN	]1.5,2.0] x ULN	]2.0,5.0] x ULN	> 5.0 x ULN
Total bilirubin	≤ ULN	]1.0,1.5] x ULN	]1.5,3.0] x ULN	]3.0,10.0] x ULN	> 10.0 x ULN
Calcium low (mmol/L)	≥ LLN	[2.00,LLN[	[1.75,2.00[	[1.50,1.75[	<1.50
Calcium high (mmol/L)	≤ ULN	]ULN,2.9]	]2.9,3.1]	]3.1,3.4]	>3.4
Total cholesterol (mmol/L)	≤ ULN	]ULN,7.75]	]7.75,10.34]	]10.34,12.92]	>12.92
Creatinine	≤ ULN	]1.0,1.5] x ULN	]1.5,3.0] x ULN	]3.0,6.0] x ULN	> 6.0 x ULN
Glucose low (mmol/L)	≥ LLN	[3.0,LLN[	[2.2,3.0[	[1.7,2.2[	<1.7
Glucose high (mmol/L)	≤ ULN	]ULN,8.9]	]8.9,13.9]	]13.9,27.8]	>27.8
Phosphate (mmol/L)	≥ LLN	[0.8,LLN[	[0.6,0.8[	[0.3,0.6[	<0.3
Potassium low (mmol/L)	≥ LLN	[3.0,LLN[	(NAP)	[2.5,3.0[	<2.5
Potassium high (mmol/L)	≤ ULN	]ULN,5.5]	]5.5,6.0]	]6.0,7.0]	>7.0
Sodium low (mmol/L)	≥ LLN	[130,LLN[	(NAP)	[120,130[	<120
Sodium high (mmol/L)	≤ ULN	]ULN,150]	]150,155]	]155,160]	>160
Triglycerides	≤ ULN	]1.0,2.5] x ULN	]2.5,5.0] x ULN	]5.0,10.0] x ULN	> 10.0 x ULN

Note:

– LLN = lower normal limit

- ULN = upper normal limit
- (NAP) = grade does not exist.

### 12.2.5.3. CTCAE v3.0 gradings for hematology tests

CTCAE version 3.0 classification is only for the below tests. For other tests, only the classification according to normal ranges will be done.

Lab test	Grade 0	Grade 1	Grade 2	Grade 3	Grade 4
Hemoglobin (g/L)	≥ LLN	[100,LLN[	[80,100[	[65,80[	< 65
WBC (giga/L)	≥ LLN	[3.0,LLN[	[2.0,3.0[	[1.0,2.0[	<1.0
Lymphocytes (giga/L)	≥ LLN	[0.8,LLN[	[0.5,0.8[	[0.2,0.5[	< 0.2
Neutrophils (giga/L)	≥ LLN	[1.5,LLN[	[1.0,1.5[	[0.5,1.0[	< 0.5
Platelet count (giga/L)	≥ LLN	[75,LLN[	[50,75[	[25,50[	< 25
INR and partial thromboplastin time	≤ ULN	]1.0,1.5] x ULN	]1.5,2.0] x ULN	>2.0 x ULN	(NAP)

Note:

- LLN = lower normal limit
- ULN = upper normal limit
- (NAP) = grade does not exist.

### 12.2.5.4. ATP III classifications

Lab test	Categories				
LDL (mg/dL)	< 100	[100,130[	[130,160[	[160,190[	≥ 190
HDL (mg/dL)	< 40	[40,60[	≥ 60		
Total cholesterol (mg/dL)	< 200	[200,240[	≥ 240		
Triglycerides (mg/dL)	< 150	[150,200[	[200,500[	≥ 500	

### 12.2.6. Handling of Urinalysis Results

Urinalysis tests for which a normal range is available will also be categorized as L, N, or H. If there is doubt on whether the result is within normal range or not, the worst-case will be taken. E.g., when the test result equals “4 to 6” and the normal range is 0-5, then the test result will be classified as abnormally high (H) if it is a post-baseline visit, and will be classified as normal (N) if it is a screening or baseline visit. The original urinalysis test result will not be used for the tables, but will only be listed.

Urinalysis tests for which no normal range is available will be listed only.

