**Table 14.3.2.4: Laboratory data up to Week 12: Shift table of the lab abnormalities per time point**

Shift table per lab test category (hematology, biochemistry, endocrine, urinalysis), lab test, treatment group and time point. The table will present the shift in abnormality (L/N/...) at worst-case and last on-treatment (other time points: not needed) versus the baseline abnormality (L/N/H). Tests without normal ranges will not be presented in this table.

Population: safety.

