**Table 14.3.2.5: Laboratory data up to Week 12: Treatment-emergent lab abnormalities per time point**

Frequency table of the treatment-emergent lab abnormalities per lab test category (hematology, biochemistry, endocrine, urinalysis), lab test, treatment group and time point (including the worst-case). A post-baseline abnormality is considered treatment-emergent if it differs from the baseline result. Tests without normal ranges will not be presented in this table.

Population: safety.

Table to be created for the Week 12 interim analysis as well.

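### A urinalysis result straddling a normal limit is scored normal at baseline and abnormal afterwards, so an unchanged result is counted as treatment-emergent

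*SAP*

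**What the plan says.** SAP section 12.2.6 sorts urinalysis tests that have a normal range into low, normal and high. For doubtful results it states: "If there is doubt on whether the result is within normal range or not, the worst-case will be taken". Its worked example is the case "when the test result equals “4 to 6” and the normal range is 0-5". That result is to be scored "abnormally high (H) if it is a post-baseline visit, and will be classified as normal (N) if it is a screening or baseline visit". It also says of the tables: "The original urinalysis test result will not be used for the tables, but will only be listed". Tests without a normal range are listed only.

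Two laboratory tables then use these classes, and both name urinalysis among their test categories:

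- Table 14.3.2.5 (treatment-emergent abnormalities, per time point and worst case): "A post-baseline abnormality is considered treatment-emergent if it differs from the baseline result".
- Table 14.3.2.4 (shift table): "The table will present the shift in abnormality (L/N/...) at worst-case and last on-treatment", set against the baseline class.

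SAP section 12.2.11 repeats both over 24 weeks as Tables 14.3.2.17 and 14.3.2.18, with the 11 adapted treatment groups. Table 14.1.3.3 tabulates the baseline laboratory classes; the only test it excludes is CRP.

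**The concern.** Treatment-emergence compares two visits, so both must be scored on one scale. Here the scale moves between them: a doubtful value gets the benefit of the doubt before treatment and loses it afterwards. Protocol section 8.8.1.4 says the shift tables are there to identify treatment-emergent abnormalities. A shift produced by the scoring rule alone does not serve that purpose.

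The rest of the laboratory scoring does not depend on the visit. SAP section 12.2.5.1 treats results reported as below or above a limit in the same way at every visit, and the CTCAE and ATP III tables call a result treatment-emergent only if it moves to a higher category on a common scale.

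What is at stake is how readable the urinalysis safety tables are. False counts raise the background in every column and make a real urinary difference harder to see in tables that carry no p-values. Table 14.3.2.5 is also an interim output, and the interim analysis is meant to support preliminary dose selection for phase III. In the other direction, Table 14.1.3.3 understates borderline findings at baseline.

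**Working it through.** **Inputs.** The scoring rule and its example come from SAP 12.2.6, and the definition of treatment-emergent from Table 14.3.2.5. The arm size is 85 and the total 595 (SAP 1.2). The scheduled post-baseline visits up to Week 12 are Weeks 1, 2, 4, 8 and 12, which makes five (SAP 12.2.9). The documents do not say how often straddling results occur.

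**Step 1: the plan's own example.** '4 to 6' against 0-5 is normal at baseline and high post-baseline, as the SAP states. High is abnormal and differs from normal, so Table 14.3.2.5 counts it, and Table 14.3.2.4 shows a shift from normal to high. For a result straddling the lower limit, the shift is from normal to low. No section exempts an unchanged result.

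**Step 2: the same example under other rules.** N is normal, H high, B borderline.

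| Rule for a straddling result | Unchanged '4 to 6' | Counted? | '4 to 6' then '8 to 10' | Counted? |
|---|---|---|---|---|
| SAP 12.2.6 | N, then H | yes | N, then H | yes |
| Abnormal at every visit | H, then H | no | H, then H | no |
| Normal at every visit | N, then N | no | N, then H | yes |
| Borderline at every visit | B, then B | no | B, then H | yes |

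Any rule that ignores the visit removes the artefact. Scoring always abnormal loses a real worsening. Scoring always normal loses a move from clearly normal to straddling. A borderline category keeps both visible.

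**Step 3: size if the result persists (illustration).** If a share q of subjects has the same straddling result at every visit on one test, the false count for that test is q × n:

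- q = 1%: 0.01 × 85 = 0.85 per arm; 0.01 × 595 = 5.95 overall.
- q = 5%: 0.05 × 85 = 4.25 per arm; 0.05 × 595 = 29.75 overall.
- q = 10%: 0.10 × 85 = 8.5 per arm; 0.10 × 595 = 59.5 overall.

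Under the last three rules in the table the count is 0.

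**Step 4: size if straddling comes and goes (illustration).** Let each visit, baseline included, straddle independently with probability p and otherwise be normal. The worst-case rate over five visits under the SAP is 1 − (1 − p)^5. The part with a straddling baseline, where the flag reflects no change, is p × [1 − (1 − p)^5]. The rest, (1 − p) × [1 − (1 − p)^5], started clearly normal.

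- p = 5%: 22.6% flagged, of which 1.1% are artefact and 21.5% a change in the reported result.
- p = 10%: 41.0% flagged, of which 4.1% are artefact and 36.9% a change.

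Here the artefact is a share p of all flags, which is far smaller than in Step 3. The size depends mainly on how persistent straddling results are.

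**The case against.** The strongest defence is that the rule is deliberate and disclosed. The SAP labels it a worst case, gives an example, and takes the same line elsewhere: missing relatedness counts as drug related, and incomplete adverse event dates are allocated to the worst case. It over-counts abnormalities rather than hiding them. Its reach is narrow. No individual stopping criterion in protocol section 8.3.4 uses urinalysis, urinalysis tests are not graded under CTCAE or ATP III, and the laboratory tables have no p-values. Affected cases can be traced, because original results are listed and Listing 16.2.11.4 shows abnormal urinalysis results with the baseline result as reference. All of this stands and limits the weight of the point. It does not make a shift correct when the subject's result has not changed. Worst-case scoring of a doubtful post-baseline value does not require the opposite scoring of the same value at baseline.

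A reader might infer that the false counts will pass for drug effects, through the pooled GLPG0634 total or the 24-week columns. The documents do not support that. Up to Week 12 the pooled total stands beside a placebo column subject to the same rule. The 24-week tables keep a continued-placebo column, and their total is across all groups (SAP 2.1.2 and 2.4.2).

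A reader might also infer that scoring by the upper end of the interval at every visit is a free remedy. It is not. It never flags a worsening from '4 to 6' to '8 to 10', and a result straddling the lower limit would be scored normal, because its upper end lies inside the range.

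**Conclusion.** The point holds as a scoring defect in descriptive safety tables. An unchanged straddling urinalysis result is counted as treatment-emergent and as a shift, in every arm.

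This rests on reading the baseline result in Table 14.3.2.5 as the baseline class. SAP 12.2.6 supports that reading by keeping the original urinalysis result out of the tables, and Table 14.3.2.4 supports it by comparing classes.

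The size cannot be fixed from the documents. At assumed persistent frequencies of 1% to 10% it is about 1 to 9 subjects per 85-subject arm and test. If straddling is intermittent it is a small share of the flags.

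Up to Week 12 no bias between randomized arms is expected, because the rule and the allocation are the same for all; the effect is added background. The 24-week columns are partly defined by Week 12 response, so that reassurance does not carry over in full, but nothing in the documents points to a direction of bias. ACR20 at Week 12 is unaffected. The change is worth making because it is cheap, not because a main conclusion depends on it.

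**What to change.** Amend SAP 12.2.6 so that a straddling result is classified in the same way at every visit, preferably in a separate borderline category used at screening, baseline and post-baseline alike. State that a post-baseline result is not treatment-emergent when its reported interval is the same as at baseline. A move from borderline to clearly abnormal is still counted, and a move from clearly normal to borderline is shown in its own row. Section 12.2.8.1 then needs a place for borderline in the worst-case ordering, between normal and abnormal.

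Apply this to Tables 14.3.2.4, 14.3.2.5, 14.3.2.17 and 14.3.2.18, and to the baseline Table 14.1.3.3.

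The cost is one extra category and derivation, and somewhat fewer abnormalities counted than under the present worst-case rule. If the sponsor prefers to keep the present rule, the minimum is a footnote giving, per arm and test, the number of treatment-emergent flags that come from unchanged straddling results.

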### 12.2.7. Last on-treatment result

Derived per parameter separately, for values as well as abnormalities.

Three last on-treatment determinations will be done, depending on the chapter of analysis:

1. Including all nonmissing post-baseline values, including “use=No” and unscheduled measurements, up to and including the Week 12 value.
2. Including all nonmissing post-Week 12 values, including “use=No” and unscheduled measurements, up to and including the Week 24 value.
3. Including all nonmissing post-baseline values, including “use=No” and unscheduled measurements, up to and including the Week 24 value.

Early discontinuation visits are considered as on-treatment visits as well.

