After becoming aware of any of the above described abnormal laboratory changes occurring at any one time, an unscheduled visit (i.e. second sequential) must occur to retest within 3 to 5 days.

 In each case, there is a need for additional investigations, such as review of ethanol, recreational drug and dietary supplement consumption; testing for acute hepatitis A, B or C infection and biliary tract imaging should be promptly discussed with the Study Medical Monitor.

 At the time of study completion or discontinuation, if a subject should exhibit elevations in serum creatinine  $\geq 33\%$  above the average of screening and baseline values, they should be re-tested every 1 to 2 weeks until the serum creatinine elevation is fully reversed to within 10% of the average of screening and baseline values.

 In each case, hormones in male subjects should be monitored monthly and if no positive dynamics is seen after 3 months from stopping GLPG0634, referral to an andrologist should be considered.

Subjects who stop study medication for any reason will not be replaced. Subjects withdrawing from the study will be encouraged to complete the same final evaluations as subjects completing the study according to the protocol, particularly safety evaluations in the subject's interest so that data can be recorded in the same way as for subjects who completed the study. Subjects are free to withdraw from the study at any time without providing reason(s) for withdrawal and without prejudice to further treatment. The reason(s) for withdrawal will be documented in the electronic case report form (eCRF).

Reasonable efforts will be made to contact subjects who are lost to follow-up. These must be documented in the subject's file.

The sponsor has the right to terminate the study at any time in case of safety concerns or if special circumstances concerning the study medication or the company itself occur, making further treatment of subjects impossible. In this event, the investigator(s) and relevant authorities will be informed of the reason for study termination.

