# **3. ANALYSIS PERIODS AND ANALYSIS TIME POINTS**

## **3.1. RELATIVE NUMBER OF DAYS**

The relative day (DY) is calculated as follows:

= Visit date – reference date + 1 day, when the visit date is on or after the reference date

= Visit date – reference date, when the visit date is before the reference date.

The reference date in the study is the first study medication intake date, which by definition has DY=1. There is no DY=0.

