### 3.3. ALGORITHM OF ALLOCATING VISITS TO TIME WINDOWS

All visits (including early discontinuation visits and unscheduled visits but excluding visits without data) will be placed into time windows according to their relative day (DY) in the study, according to the following allocation table:

Time point label	Target day	Interval lower bound	Interval upper bound
Screening (3)	NA	NA	NA
Baseline (1)	NA	NA	NA
Week 1	8	2	11
Week 2	15	12	21
Week 4	29	22	42
Week 8	57	43	70
Week 12	85	71	98
Week 16	113	99	126
Week 20	141	127	154
Week 24	169	155	182
>Week 24 (2)	NA	183	+∞
Follow-up (3)	7-10 days after last visit	NA	NA

(NA = not applicable).

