#### 12.4.4. Last on-treatment result

Derived per parameter separately, for values as well as abnormalities.

Three last on-treatment determinations will be done, depending on the chapter of analysis:

1. Including all nonmissing post-baseline values, including “use=No” and unscheduled measurements, up to and including the Week 12 value.
2. Including all nonmissing post-Week 12 values, including “use=No” and unscheduled measurements, up to and including the Week 24 value.
3. Including all nonmissing post-baseline values, including “use=No” and unscheduled measurements, up to and including the Week 24 value.

Early discontinuation visits are considered as on-treatment visits as well.

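### The SAP defines the last on-treatment laboratory value without the last-dose date, so off-drug creatinine and male-hormone retests can be reported as on-treatment

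*SAP*

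**What the plan says.** - **SAP 12.2.7** makes three last on-treatment determinations (period 1, period 2, whole study). The first takes every nonmissing post-baseline value, including results flagged as not used "and unscheduled measurements, up to and including the Week 12 value". The other two run to the Week 24 value. No condition refers to the last dose.
- **SAP 12.2.7 and 12.4.4** (vital signs) both add: "Early discontinuation visits are considered as on-treatment visits as well".
- **SAP 3.1 and 3.3**: "The reference date in the study is the first study medication intake date", and "All visits (including early discontinuation visits and unscheduled visits but excluding visits without data) will be placed into time windows" on that day count. Only screening and Follow-up visits keep their eCRF label.
- **Protocol 8.3.4, footnote 2**: when creatinine is at least 33% above the screening/baseline average at completion or discontinuation, "they should be re-tested every 1 to 2 weeks until the serum creatinine elevation is fully reversed", meaning to within 10% of that average.
- **Protocol 8.3.4, footnote 3**: "hormones in male subjects should be monitored monthly and if no positive dynamics is seen after 3 months from stopping GLPG0634" (the sentence then raises specialist referral). Three months is the referral point; no end to the monthly testing is given.
- **SAP 12.2.9** lists last on-treatment as a time point in the laboratory tables. The shift tables show only that result and the worst case.

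**The concern.** A result labelled on-treatment should describe the subject while taking drug. The protocol generates off-drug samples in the subjects of most interest, those with raised creatinine or depressed male hormones at discontinuation. Creatinine retesting ends on recovery, so the last sample in a completed series is a recovered one by design. If such samples enter the derivation, recovery after stopping cannot be told apart from resolution on drug.

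The SAP's other choices suggest this was not intended. Section 12.2.8 adds the Follow-up value to the worst case, whereas 12.2.7 does not add it to last on-treatment. Post-treatment data are thus kept out by one route and admitted by another. Section 3.2 already uses the last-dose date to close the adverse-event periods.

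**Working it through.** The documents state no figure for this rule, so there is none to reproduce. The check applies the rule as written.

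**Inputs.** SAP 3.3 windows: Week 8 is Days 43–70 (target 57), Week 12 is 71–98 (85), Week 16 is 99–126 (113), Week 20 is 127–154 (141), Week 24 is 155–182 (169). SAP 3.4: the visit closest to target is selected, and ties go to the later visit. Retest intervals follow protocol 8.3.4: 7 or 14 days for creatinine, 28–30 days for hormones.

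**Assumptions.** The EDV falls on the stop day and carries the toxic value. Retests are stored as unscheduled samples.

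**1. Can a post-stop retest fall in the last on-treatment range?** For stop day *s*, interval *k* and limit *L*, the first retest qualifies if *s* + *k* ≤ *L*. Stop days 8–84 give 77 possibilities and stop days 86–168 give 83. The SAP does not say whether the limit is the window end or the target day, so both are shown.

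| Interval | Period 1, L = 98 | Period 1, L = 85 | Period 2, L = 182 | Period 2, L = 169 |
|---|---|---|---|---|
| 7 days | 77/77 | 71/77 | 83/83 | 77/83 |
| 14 days | 77/77 | 64/77 | 83/83 | 70/83 |
| 28 days | 63/77 | 50/77 | 69/83 | 56/83 |
| 30 days | 61/77 | 48/77 | 67/83 | 54/83 |

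Creatinine qualifies for all stop days on the window-end reading and for 83–93% on the target-day reading. Hormones qualify for 79–83% and 62–67%. These are shares of possible stop days, not of patients.

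**2. Is the stop-day value displaced in its own weekly row?** Less often. On the window-end reading, for creatinine, 17–26 of 77 (22–34%) in period 1 and 24–33 of 83 (29–40%) in period 2. For hormones it is 0, because monthly retests land in later windows and fill those rows instead. Example: stop Day 57, retests at Days 87, 117 and 147, which become Weeks 12, 16 and 20.

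**3. Are these samples off drug?** Protocol 6.7 gives a parent half-life of 5 to 11 hours. Seven days is 168 h, so 168/11 = 15 to 168/5 = 34 half-lives. The metabolite's half-life is not given.

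**4. Illustration (assumed values).** Creatinine 70 at baseline (and as the pre-dose average); 112 at Day 57 (112/70 − 1 = +60%); 110 at Day 61 (+57%, confirmed, drug stopped); 88 at Day 75 (+26%); 74 at Day 89 (+6%). As written, last on-treatment is 74 (+6%). Day 89 is also the Week 12 value, since |89 − 85| = 4 is less than |75 − 85| = 10. Limited to samples at or near the last dose, last on-treatment is 110 (+57%).

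**5. Does the worst case cover this?** Not for every creatinine rise. SAP 12.2.8 is derived for abnormalities only, using normal limits and, for CTCAE, multiples of ULN. The stopping rule is relative: more than 50% over the subject's own average. A +60% rise stays at or below ULN whenever baseline ≤ ULN/1.6 = 0.625 × ULN. Such a subject is normal and Grade 0 at worst case, and the rise shows only in the continuous summaries.

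**6. Effect on an arm mean (assumption).** If *m* of 85 subjects enter at +10% instead of +50%, the mean percent change in creatinine falls by 40 × *m*/85 points: 0.5 for *m* = 1 and 1.9 for *m* = 4. The documents give no value for *m*.

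**The case against.** The strongest reply is that nothing is hidden and that the samples may never reach the dataset.

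**Worst case.** A reader might infer that the toxicity disappears from the report. It does not. SAP 12.2.8 takes the worst case over all post-baseline values, unscheduled and Follow-up included, and shows it beside last on-treatment in the shift tables and in the treatment-emergent tables. For inhibin B and testosterone, Table 14.3.2.12 shows the lowest value. Events leading to discontinuation and flagged stopping criteria have their own tables. This stands, except for the within-normal-range creatinine rise in step 5.

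**Data capture.** A subject meeting a stopping rule is withdrawn, has an EDV, and has a Follow-up visit 7 to 10 days later. With a Day 57 stop and EDV, Follow-up falls on Days 64–67, so the monthly hormone tests all come after the last scheduled visit. A first creatinine retest may coincide with Follow-up, which is neither windowed nor included by 12.2.7. The documents do not say that later retests go to the central laboratory or into the database as unscheduled visits. This stands and makes the effect conditional.

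**Scope.** A reader might extend the point to all laboratory shift tables. Table 14.3.2.10 covers lipids only, for which no post-stop retest is required, and the CTCAE lists behind Table 14.3.2.7 contain no hormone. Counting the EDV as on-treatment is an explicit choice, though the protocol sets no interval between last dose and EDV.

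**Conclusion.** The point holds in limited form. SAP 12.2.7 attaches an on-treatment label to values that need not be on treatment, and SAP 3.3 can place the same values in weekly rows. This is a stated rule that can return a wrong value.

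The effect is limited to creatinine and male hormones. It bears on the continuous summaries (Tables 14.3.2.1 to 14.3.2.3, also produced for the Week 12 interim, and their 24-week repeats), the last on-treatment column of Table 14.3.2.4, and creatinine in Table 14.3.2.7. It depends on retests being stored as unscheduled samples. The number of subjects is unknown and probably small, and the primary endpoint is untouched.

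It would go too far to say that every subject stopped for creatinine enters near baseline. Retesting can run past Day 98 or 182, leaving a partly recovered value. The 10% target also refers to the screening/baseline average, whereas SAP 12.2.4 uses the last pre-dose sample. Nor can a misclassification rate for the shift tables be given, because a rise of more than 50% need not change a normal-range category or a CTCAE grade.

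**What to change.** In SAP 12.2.7, define last on-treatment as the last nonmissing value dated on or before the last study-drug intake plus a small fixed number of days, with the same allowance applied to the EDV. Flag later samples as post-treatment, do not select them for the SAP 3.3 weekly windows in the laboratory safety tables, and show them in a separate row so that recovery is reported as recovery. Use the same wording in 12.4.4 for consistency; the protocol requires no post-stop retest of vital signs. Leave the worst case unchanged.

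The cost is a few lines of SAP text and one date comparison in the derived dataset. The last-dose date is already collected and used in SAP 3.2 and 7.8.1. The downside is a slightly smaller N at later weekly time points.
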